10.2 Data Management

Data will be double-keyed and validated using ClinPlus (DZS Software Solutions), which directly generates SAS® data sets, Clinical Data Interchange Standards Consortium (CDISC) format. After resolution of double-key discrepancies and a combination of manual and automated data review

procedures, the final data sets will be subject to a Quality Assurance audit. SAS® programs for data analysis and presentation will be applied to secure validated data sets.

10.3 Retention of Documents

Essential documents, as listed below, must be retained in a secure place by the Investigator for a minimum of 5 years from completion of the study, or as long as needed to comply with national and international regulations (generally 2 years after discontinuing clinical development or after the last marketing approval). Amzell B.V. will notify the Investigator(s)/institution(s) when the study-related records are no longer required. The Investigator agrees to adhere to the document retention procedures by signing the protocol.

Essential documents include:

- The study protocol and any amendments,
- IRB approvals for the study protocol and all amendments,
- All e-source documents and laboratory records,
- eCRF originals or copies,
- Subjects' eICFs (with study number and title of study),
- FDA Financial Disclosure Forms
- Site Delegation of Duties Log
- IP Accountability Documentation
- FDA form 1572 (as required)
- Any other pertinent study document (i.e., correspondence, study report[s]).

All study related documents will be stored at either the study site at [name] in a secured room accessible only to TKL employees, or at a specified offsite location that provides a secure environment with burglar/fire alarm systems, camera detection, and controlled temperature and humidity. Originals or copies of the eCRFs, source documents, correspondence, IRB documents, study reports, etc., will be available for the Sponsor's review on the premises of TKL. Amzell B.V. must be informed of the offsite location at the time the documents are transferred to long-term storage.

No study site document may be destroyed without prior written agreement between the Investigator and Amzell B.V. Should TKL choose to assign the study documents to another party or move them to another location, Amzell B.V. must be notified.

10.4 Confidentiality of Subject Data

The Investigator will preserve the confidentiality of the subjects' data. eCRFs and other documents submitted to Amzell B.V. will reference subjects only by an anonymized subject ID, which uniquely identifies the subject in the context of the study. The Investigator will maintain

documents not meant for submission to the sponsor, e.g., the confidential subject identification code and the signed informed consent forms, in strict confidence. All data are subject to monitoring, audits and inspection. If, as an exception, it is necessary for safety or regulatory reasons to identify the subject, both Amzell B.V. and the Investigator are bound to keep this information confidential.

10.5 Clinical Monitoring Plan (CMP)

The CMP identifies the monitoring schedule and the rationale for the frequency and type of monitoring visits. Since this study is using Direct Data Entry (DDE), in addition to agreed-upon source data verification (SDV), on-site monitoring visits will be limited to assuring that the site understands and is following the protocol, is adequately monitoring subject safety, and is managing the drug supply. The CMP also provides details on the use of risk-based monitoring and source document verification. If the monitor is not allowed access to any e-source records during source document verification, certified printouts provided by the site can be used. In addition to on-site monitoring, monitors will perform remote monitoring, electronically reviewing data in near real-time.

| Communication | Timeframe |
|---|--|
| Site initiation visit (SIV) | The site must have a SIV (if SSV not performed). |
| First monitoring visit | See CMP. |
| Interim monitoring visits (IMV) | As specified in the CMP |
| Closeout visit (COV) | The site must have a COV. |
| Site Update and Monitoring Calls | Monitors will contact the site as needed via email or telephone, based on review of site activity and the quality of data entry and DDC. |
| Teleconferences between the site and Contract Research Organization (CRO) | Monitors will schedule teleconferences as appropriate to discuss the overall study status and to discuss study-wide related issues. |

| Communication | Timeframe |
|--|---|
| Initiation, Monitoring and Closeout Visit Reports | 
Interim monitoring visits can be performed on-site or online. On-site visits are preceded by a confirmation letter sent to the site. The confirmation letter must outline the date, time and purpose of the monitoring visit
 
Monitors will route all online, Initiation, Monitoring and COV Reports for signature to their supervisor(s). The TKL Project Manager will review the report and enter comments if needed.
 
Following the completion of an on-site monitoring visit report, the monitor provides feedback to the site, identifying any outstanding issues from the visit.
 |
| Study updates, Protocol Amendments, etc. | Will be forwarded to site during study. |
| Adverse Events (AE) and Serious Adverse Events (SAE) | The primary method for reporting the event consists of entering data into the AE and SAE forms and completing the MedWatch FDA Form 3500A. |

10.6 Audit Procedures

In addition to the routine monitoring procedures, the study site will be audited in depth for study Quality Assurance by Amzell B.V., an external auditor on behalf of the Sponsor, and maybe by a regulatory authority. This audit may include a review of all source documents, drug records, reserve sample retention records and original eCRFs at the study unit used in the study. Subject confidentiality will be maintained at all times and consent for this will be obtained before entry of the subject into the clinical study. If an inspection is requested by a regulatory authority, the Investigator must immediately inform Amzell B.V. that this request has been made.

10.7 Investigational Medicinal Product (IMP)

Monitors will verify that the Investigator maintains accurate and adequate records including dates of treatment, duration of treatment, and appropriate follow-up. Monitors will perform IMP and reserve sample accountability and verify storage conditions of the IMP and reserve samples (secure location, temperature logs, etc.) in accordance with manufacturers' instructions. Monitors will verify that the site has an adequate supply for ongoing and new subjects.

During the course of the study, the monitor is responsible for assuring the accountability and reconciliation of the IMP. To assist with this, the monitor will review or perform the following, as appropriate:

- IMP Receipt and return of delivery note(s)
- Reserve Sample Request/Log
- All used and unused IMP (except for the reserve IMP samples retained on site) will be sent by the study site for destruction in accordance with national requirements:
 - Certificate of destruction to be provided to Amzell once done.

10.8 Laboratory Samples and Analysis

Laboratory samples, both for clinical safety and PK analysis, will be processed through a local laboratory (LabCorp for safety analysis and Sannova for PK analysis) and the results will be sent to TKL.

Specific details for PK laboratory sample processing are described in the Sannova Sample Analysis Plan. Specific details for clinical laboratory sample handling (clinical chemistry, hematology, serology and urinalysis samples) are detailed in the LabCorp Laboratory Manual.

11. CHANGES IN CONDUCT OF THE STUDY

11.1 Protocol Amendments

Any changes or additions to this clinical study protocol require a written protocol amendment that must be approved by Amzell B.V. and the Investigator before implementation. Amendments significantly affecting the safety of subjects, the scope of the investigation or the scientific quality of the study, require additional approval by the appropriate IRB for the study site. A copy of the written approval of the IRB, which becomes part of the protocol, must be given to the Sponsor. Examples of amendments requiring such approval are:

1. An increase in study product dosage or duration of product exposure of subjects,
2. A significant change in the study design,
3. An increase in the number of invasive procedures to which subjects are exposed, and
4. Addition or deletion of a test procedure for safety monitoring.

These requirements for approval should in no way prevent any immediate action from being taken by the Investigator or Amzell B.V. in the interests of preserving the safety of all subjects included in the trial. If an immediate change to the protocol is felt to be necessary by the Investigator and is implemented by him/her for safety reasons, Amzell B.V. should be notified immediately and the IRB at the center should be informed within 10 working days.

Amendments affecting only administrative aspects of the study do not require formal protocol amendments or IRB approval, but the IRB of each center must be kept informed of such administrative changes. Examples of administrative changes not requiring formal protocol amendments and IRB approval that can be treated as administrative amendments include:

1. Changes in the staff used to monitor studies (e.g., Amzell B.V. staff versus TKL), and
2. Minor changes in the packaging or labeling of the IP.

11.2 Deviations from the Protocol

Deviations from the planned study conduct are not permitted; any deviations and changes in study conduct must be reported to Amzell B.V., the IRB, and noted in the final clinical study report.

11.3 Premature Study Termination

Both Amzell B.V. and the Investigator (after consultation with Amzell B.V.) reserve the right to terminate or suspend the study at any time. Should this be necessary, the procedures will be arranged on an individual study basis after review and consultation by both parties. It is the responsibility of the Investigator to notify the IRB of the termination/suspension and the reason(s). In terminating the study, Amzell B.V. and the Investigator will ensure that adequate consideration is given to the protection of the subjects' interests.

12. REPORTING AND PUBLICATION

12.1 Clinical Study Report

The data and information collected during this study will be reported in a Clinical Study Report prepared by the TKL.

12.2 Confidentiality and Ownership of Study Data

Any confidential information relating to the IMP or the Study, including any data and results from the study will be the exclusive property of Amzell B.V. The Investigator and any other persons involved in the study will protect the confidentiality of this proprietary information belonging to Amzell B.V.

12.3 Publication Policy

No presentation or publication of data from this study can be initiated without the explicit written consent and in direct collaboration with Amzell B.V.

13. ETHICAL AND REGULATORY ASPECTS

13.1 Institutional Review Board (IRB)

Before implementing this study, the protocol, the proposed ICF and other information to subjects, must be reviewed by a properly constituted IRB. A signed and dated statement that the protocol and informed consent have been approved by the IRB must be given to TKL and Amzell B.V. before study initiation. The name and occupation of the chairman and the members of the IRB must also be supplied to TKL and Amzell B.V. This committee must also approve any amendments to the protocol, other than administrative ones, and a signed and dated statement of approval must be sent to Amzell B.V. prior to initiation of the amendment procedures.

13.2 Ethical Conduct of the Study

This study must be carried out in compliance with the protocol and in accordance with TKL's standard operating procedures (SOPs). These are designed to ensure adherence to good clinical practice (GCP) guidelines, as described in:

- International Conference on Harmonisation (ICH) Tripartite Guidelines for GCP 1996. Directive 91/507/, The Rules Governing Medicinal Products in the European Community.
- United States 21 Code of Federal Regulations dealing with clinical studies (including parts 50 and 56 concerning informed consent and IRB).
- Declaration of Helsinki, concerning medical research in humans (Recommendations Guiding Physicians in Biomedical Research Involving Human Subjects, Helsinki 1964 and amendments).

The Investigator agrees, when signing the protocol, to adhere to the instructions and procedures described in it and thereby to adhere to the principles of GCP that it conforms to.

13.3 Subject Information and Consent

The Investigator or designee must explain to each subject (or legally authorized representative) the nature of the study, its purpose, the procedures involved, the expected duration, the potential risks and benefits involved, and any discomfort it may entail. Each subject must be informed that participation in the study is voluntary, that he/she may withdraw from the study at any time, and that withdrawal of consent will not affect his/her subsequent medical treatment or relationship with the treating physician.

This informed consent should be given by means of a standard written statement, written in non-technical language. The subject should read and consider the statement before signing and dating it, and he/she should be given a copy of the signed document. If written consent is not possible, oral consent (assent) can be obtained, if witnessed by a signed statement from one or more people not involved in the study, mentioning why the subject was unable to sign the form.

No subject can enter the study before a dated informed consent has been obtained from him/her, or his/her legally authorized representative.

The ICF is considered to be part of the protocol and must be submitted by the Investigator with it for IRB approval. TKL will supply a proposed ICF to be approved by Amzell B.V. TKL's ICF contains all elements (information or statements), as per ICH E6(R2) section 4.8.10 and 21 CFR § 50.25[c], and is presented in a non-technical language that is understandable to the subject. Any changes to the proposed consent form suggested by the Investigator must be agreed to by TKL and Amzell B.V. before submission to the IRB, and a copy of the approved version must be provided to Amzell B.V. after IRB approval.

14. ARCHIVING

14.1 Trial Master File

TKL will archive the trial master file in accordance with ICH-GCP, applicable regulatory requirements and TKL SOP.

1. INTRODUCTION

Study AMZ001-008 will be a Phase 1 pharmacokinetic (PK) and safety clinical trial comparing 2 dose levels of AMZ001, an experimental formulation of diclofenac sodium gel, with the marketed over-the-counter (OTC) formulation Voltaren Arthritis Pain 1% Gel (GSK Consumer Healthcare). The two doses of the new formulation were selected based on the outcomes of a previous PK and safety study (AMZ001-005) to provide systemic diclofenac exposure when applied once daily comparable to 4 daily applications of Voltaren Arthritis Pain gel. Voltaren Arthritis Pain gel is indicated for 4 daily applications for the topical treatment of arthritis pain. Study AMZ001-008 will characterize the rate and extent of diclofenac absorption from the two different doses of AMZ001 compared to Voltaren Arthritis Pain gel. This Statistical Analysis Plan (SAP) is based on the study protocol dated 23 March 2023.

2. STUDY OBJECTIVES

The primary objective of the study is to compare the bioavailability of 2 dose levels (6 mL [5.5 g] and 8 mL [7.4 g]) of AMZ001 (diclofenac sodium gel 3.06%) applied once daily as 3 mL and 4 mL per knee on both knees and one dose level of Voltaren Arthritis Pain Gel (32 g, diclofenac sodium gel 1%) applied 4 times daily as 4 g per knee on both knees after repeated topical administrations in healthy subjects for 7 days.

Secondary objectives are to determine the PK profiles of the 3 study products and to assess their safety and tolerability under the conditions of their intended use.

3. STUDY DESIGN

The study will follow a randomized open-label 3-way crossover design in which every subject will receive all 3 study products in one of the 6 possible treatment sequences. During each of the 3 study periods, subjects will receive daily treatment for 7 successive days. Subjects will be confined to the study site under supervision from the evening before the first treatment application of the period until 24 hours after the last application. The treatment periods will be separated by 2 washout periods of 21 days each.

Treatments and treatment sequences are defined as follows.

Sequence Number	Period 1	Period 2	Period 3
1	A	B	C
2	B	C	A
3	C	A	B
4	B	A	C
5	A	C	B
6	C	B	A

Treatment A: 6 mL (5.5 g) daily, 2 doses of 1.5 mL on each knee QD

Treatment B: 8 mL (7.4 g) daily, 4 doses of 1 mL on each knee QD

Treatment C: Voltaren Arthritis Pain Gel, 32 g daily, 4 g on each knee 4 times daily

At each application, subjects will spread the gel directly to pre-defined treatment areas of approximately 400 cm² (Treatments A and C) and 500 cm² (Treatment B) on each knee following prescribed application instructions.

On Day 1 and Day 7, blood samples for PK analyses will be collected within 1 hour prior to application and at 2, 4, 6, 8, 10, 12, 14, 16, 18, 20, and 24 hours after application. Trough level samples will be collected before application on Days 3, 4, 5, and 6. At the end of Period 3, additional PK blood samples will be taken at 3, 4, and 5 weeks after the last application in order to characterize and to compare the elimination kinetics of the 3 study products.

Subjects will be healthy males or females 18 to 65 years old, determined by the Investigator to be in good general health based on medical history and physical examination, including vital signs, 12-lead ECG, and clinical laboratory tests. Approximately 75 subjects will be randomized to ensure at least 60 evaluable subjects.

4. HARDWARE AND SOFTWARE

Statistical analysis will be performed following TKL standard operating procedures (SOPs) and on the TKL computer network. All statistical analyses will be performed using SAS Version 9.4 or higher with program code prepared specifically for the project by qualified TKL statisticians and SAS programmers.

The SAS programs will generate rich-text-formatted (RTF) output with the “RTF” extension using the SAS Output Delivery System (ODS). The summary tables and listings will be

formatted using the Times New Roman font. The RTF output is included in report documents prepared with Microsoft Word and converted to PDF format without typographical change.

Study data tabulation model (SDTM) data sets and required analysis data model (ADaM) data sets will be created and taken as input to validated SAS programs to generate the report-ready tables, listings, and figures. Each output display will show the names of the data sets and SAS program used to produce it. Upon completion of the study report, the data sets will be provided to the sponsor as SAS XPT transport files with define.xml files including details of all derivations and imputations used.

5. STATISTICAL DATA REVIEW

Data verification activities to be performed prior to delivery of the SAS data sets to the project statistician are described in the approved Data Management Plan (DMP). After completion of the data verification activities, the SAS data sets will be reviewed by the project statistician along with documentation of any unresolved queries and data conventions applied that are not fully explained in the data or in the DMP. The project statistician will perform completeness and self-consistency checks of the study data. These checks will be selected to ensure the self-consistency of dates and events in the subject record, the consistency of all reported data values with expected ranges, and, if not within range, the presence in the subject record of explanatory comments or other corroborative data. Overall, each subject's record in the study database must convey a full but concise description of the subject's experience with respect to protocol-specific events. Questions will be issued to the Data Manager and resolved before closure of the database.

6. DATABASE CLOSURE

After completion of all data review procedures, validation of the project database (ie, all those activities and operations designed and performed to ensure that the database is a complete and accurate representation of protocol-specific events), and approval of the data review document by the study sponsor, the clinical database will be closed (ie, “locked”). Any change to the clinical database after this time will require written authorization, with explanation, by the Sponsor and the Biostatistician, in conformance with TKL SOPs.

7. SAMPLE SIZE DETERMINATION

The sample size of 60 subjects was determined to provide 80% power in a standard two 1-sided test of bioequivalence assuming an intrasubject coefficient of variation (CV) of 61% and a true

ratio of geometric means 1.05. These assumptions were derived by averaging historical data and the results of Study 000084. For the purposes of the sample size estimate, bioequivalence was defined as the inclusion of a 2-sided 95% confidence interval (1-sided 97.5%) on the ratio of geometric means (Test/Reference) within the equivalence margin of 80% to 125%. The wider confidence interval was used to account for the multiplicity of tests planned in the study. The plan to enroll 75 subjects assumes that 20% of enrolled subjects will be incomplete or not evaluable.

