Secondary endpoint(s):

- The PK parameters C_{max} , minimum plasma drug concentration (C_{min}), time to reach maximum (peak) plasma concentration following drug administration (T_{max}), time to reach minimum plasma concentration following drug administration (T_{min}), terminal disposition rate constant (λ_z), the time it takes for the plasma drug concentration to decrease by half ($T_{1/2}$), average plasma drug concentration (C_{av}) and peak-to-trough fluctuation (PTF) of the two different dose levels of AMZ001 and one dose of Voltaren Arthritis Pain Gel will be calculated. The PK parameters for Day 1 will also be calculated and considered as secondary endpoints.

Safety endpoint(s):

- Adverse Events (AEs); including serious, treatment emergent, adverse drug reactions (ADRs)
- Local and systemic tolerability

STATISTICAL METHODS:

Below is a summary of the statistical analysis methods. For more details on each analysis, please refer to [Section 9](#).

Sample Size: Based on the assumption (averaging historical data and 000084 result), intra-subject coefficient of variation (CV) was 61%. A total of sixty (60) evaluable subjects will achieve 80% power using 95% confidence interval (CI), to account for multiplicity. The true ratio that was used in the sample size calculation was 1.05. Enough healthy adults will be screened to randomize approximately seventy-five (75) subjects to ensure sixty (60) evaluable subjects, assuming a 20% dropout and non-evaluable rate. All subjects will receive all 3 treatments over the course of the 3 study periods. Subjects will be randomized to one of the 6 possible sequences of 3 treatments, as specified in the design section above, to provide adequate information about the PK parameters and safety for the purposes of this study.

Statistical analysis: Descriptive statistics will be used to summarize the baseline demographic information.

Safety analysis: Descriptive statistics will be used to summarize AEs, laboratory data, physical examinations, and vital signs.

Pharmacokinetic (PK) Analysis: PK analysis will be performed using SAS® system.

PK parameters area under the plasma concentration-time curve from time zero to time t ($AUC_{0-\tau}$) and C_{max} will be compared across treatment groups using an analysis of variance (ANOVA) model. The ratio of the PK parameters will be estimated along with 90% confidence limits to assess comparable bioavailability.

SIGNATURE PAGE

AMZ001 (Diclofenac Sodium Gel 3.06%)

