9.1 Determination of Sample Size

Based on the assumption (averaging historical data and Phase 1 Study 000084 study results), intra-subject coefficient of variation (CV) was 61%. A total of sixty (60) evaluable subjects will achieve 80% power using 95% confidence interval (CI), to account for multiplicity. The true ratio that was used in the sample size calculation was 1.05. Enough healthy adults will be screened to randomize approximately seventy-five (75) subjects to ensure sixty (60) evaluable subjects, assuming a 20% dropout and non-evaluable rate. All subjects will receive all 3 treatments over the course of the 3 study periods. Subjects will be randomized to one of the 6 possible sequences of 3 treatments, as specified in the design in [Figure 1](#), to provide adequate information about the PK parameters and safety for the purposes of this study.

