9.7.2 Pharmacokinetics (PK)

PK analysis will be performed using the SAS® system. PK parameters assessed at Day 1 and Day 7 will include $AUC_{0-\tau}$, C_{max} , C_{min} , C_{av} , PTF, T_{max} , T_{min} , λ_z , and $T_{1/2}$, and will be presented in listings for individual subjects and summarized in tables and figures.

PK parameters $AUC_{0-\tau}$ and C_{max} will be compared across treatment groups using an analysis of variance (ANOVA) model. The ratio of the PK parameters will be estimated along with 90% confidence limits to assess comparable bioavailability.

Please refer to the SAP for detailed analysis method.

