The log-transformed parameters $AUC_{0-\tau}$ and C_{max} for Day 1 and Day 7 will be compared across treatments using the analysis of variance (ANOVA) model with effects of sequence, subject within sequence, period, and treatment. Sequence will be tested using subject within sequence for error. Period and treatment will be tested against the residual error. Least squares geometric means and standard errors will be provided by treatment. The ratio of geometric means will be determined for Treatments A and B using Treatment C as Reference. A 90% 2-sided confidence interval (ie, two 95% 1-sided tests) will be calculated. The object of the tests is to determine comparability of the rate (C_{max}) and extent ($AUC_{0-\tau}$) of absorption after a single dose and after a week of daily dosing.

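### The stated 80% power does not follow from the stated inputs: 60 subjects, CV 61%, true ratio 1.05 and limits of 80–125% give about 14% with the 95% CI used for sizing, or about 36% with the 90% CI planned for analysis

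*SAP*

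**What the plan says.** SAP section 7 says that "The sample size of 60 subjects was determined to provide 80% power in a standard two 1-sided test of bioequivalence". The inputs are a within-subject CV of 61% and a true ratio of geometric means of 1.05, both obtained by averaging historical data with the results of Study 000084. For sizing, success means that a two-sided 95% interval for Test/Reference lies "within the equivalence margin of 80% to 125" percent. The wider interval is there to allow for multiple tests.

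Protocol 9.1 makes the same claim: "A total of sixty (60) evaluable subjects will achieve 80% power using 95% confidence interval (CI), to account for multiplicity". It adds: "The true ratio that was used in the sample size calculation was 1.05". The synopsis repeats both statements. Neither place gives the equivalence limits; only SAP section 7 does. None of the three places says whether the 61% describes AUC or Cmax.

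On design, SAP section 3 says that "every subject will receive all 3 study products in one of the 6 possible treatment sequences", so there is no replication of any product within a subject.

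The analysis uses a different interval. SAP 10.5 says: "A 90% 2-sided confidence interval (ie, two 95% 1-sided tests) will be calculated". Protocol 9.7.2 agrees: "The ratio of the PK parameters will be estimated along with 90% confidence limits to assess comparable bioavailability". Neither section states limits.

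**The concern.** A CV of 61% is high for a non-replicated crossover judged against 80–125%, and 60 subjects looks far too few for 80% power. This power statement is the only justification given for 60 evaluable (75 randomized) subjects.

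It tells the reader that, at a true ratio of 1.05, each comparison has a 4 in 5 chance of its interval falling inside the limits. If the real chance is much lower, an interval that crosses a limit says little about whether exposures differ, because imprecision is the likelier cause. A reader relying on 80% power would take it as evidence that the products are not comparable.

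**Working it through.** **Inputs**

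- Evaluable subjects n = 60; CV = 0.61; true ratio 1.05; limits 0.80 and 1.25; 95% CI, i.e. one-sided 0.025 (SAP section 7).
- 90% CI, i.e. one-sided 0.05, for the analysis (SAP 10.5, Protocol 9.7.2).
- Three treatments, three periods, six sequences, each treatment once per subject (SAP section 3).
- Log-scale ANOVA with sequence, subject within sequence, period and treatment (SAP 10.5). Residual df = 2n − 4 = 116.

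**The plan's own figures.** The dropout step reproduces: 60 / (1 − 0.20) = 75. The 80% does not.

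**Step 1: standard error**

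- Within-subject log variance = ln(1 + 0.61²) = 0.3163, so the log SD is 0.562.
- SE of a treatment difference = √(2 × 0.3163 / 60) = 0.1027.

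**Step 2: check by hand.** The limit is ln(1.25) = 0.223, and the assumed true difference is ln(1.05) = 0.049.

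- 95% CI: half-width about 0.203. If the estimated SD equals 0.562, the interval fits only when the observed ratio is within exp(±0.020), about 0.98–1.02. The assumed true ratio of 1.05 lies outside that window.
- 90% CI: half-width about 0.170, window about 0.95–1.05. The assumed true ratio sits at its edge.

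**Step 3: normal approximation.** Power ≈ Φ[(ln 1.25 − ln 1.05)/SE − z] + Φ[(ln 1.05 − ln 0.80)/SE − z] − 1.

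- 95% CI, z = 1.96: 0.397 + 0.754 − 1 = 0.151.
- 90% CI, z = 1.645: 0.521 + 0.842 − 1 = 0.363.

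**Step 4: exact power**, integrating over the chi-square distribution of the residual variance with 116 df: **14.1%** (95% CI) and **35.6%** (90% CI). A simulation of 1,000,000 runs gave 14.1% and 35.5%.

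**Step 5: can another reading recover 80%?**

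| Variant | 95% CI | 90% CI |
|---|---|---|
| As stated, n = 60 | 14.1% | 35.6% |
| 58 df (two-period crossover) | 13.8% | 34.8% |
| True ratio 1.00 | 15.8% | 39.4% |
| All 75 evaluable | 30.7% | 50.0% |
| 0.61 taken as the log SD | 4.8% | 24.8% |
| Factor 2 dropped from the variance (wrong for this design) | 62.4% | 75.2% |
| 0.61² = 0.372 taken as the log SD (wrong) | 69.9% | 80.8% |

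Only the last row comes near 80%. It misuses the CV and needs the 90% interval, whereas the sizing text specifies 95%. It may be coincidence.

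**Step 6: what would give 80%, changing one input at a time**

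| Input changed | 95% CI | 90% CI |
|---|---|---|
| Evaluable subjects | 168 | 134 (138 as a multiple of six) |
| CV, at n = 60 | about 34% | about 39% |
| Limits, at n = 60 | about 70–142% | about 73–137% |

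**Step 7: precision at n = 60.** exp(0.2034) = 1.23 for the 95% CI and exp(0.1703) = 1.19 for the 90% CI.

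**The case against.** The strongest reply is that the check shows inconsistency, not low power. The 61% comes from data that the reader cannot see. If the CV was mistranscribed (about 34% would fit) or wider limits were used (about 70–142% would fit), the 80% could be right. This stands as a limit on the conclusion: the 14% and 36% are conditional on the stated inputs. It does not defend the text. SAP section 7 calls the test standard and states 80–125%, and neither document mentions scaled limits or replication.

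A second reply is that the 36% belongs to a test the plan never defines, since it joins the SAP section 7 limits to the SAP 10.5 interval. That is a fair description. The direct check of SAP section 7 is the 14%; the 36% shows that moving to the analysis interval does not rescue the claim. Having one interval for sizing and another for analysis is a separate inconsistency.

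A third is that this is a Phase 1 study whose output is ratios with intervals, and a wrong power figure biases none of them. That is true, and it limits the harm to the justification of the sample size and the reading of an inconclusive result. But the trial was sized on a formal bioequivalence criterion, and Protocol 3.5.4 says the objective is to identify one dose.

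**Conclusion.** The concern holds. The inputs in SAP section 7 and the 80% power cannot all be correct. Taking the inputs as stated, power is about 14% with the 95% CI, about 1 in 7, so 80% overstates it 5.7-fold (0.80 / 0.141). With the 90% CI it is about 36%, just over 1 in 3, a 2.2-fold overstatement (0.80 / 0.356).

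Both figures are for one AMZ001 dose against Voltaren on one parameter. Requiring both AUC and Cmax, or both doses, cannot raise the chance of success. They assume 60 subjects with complete data, log-normal parameters and a common within-subject variance. Even with all 75 randomized subjects evaluable, power is 31% or 50%. The documents do not show which figure is in error. The planned ANOVA and its interval estimates are unaffected.

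**What to change.** 1. Trace the sizing calculation: which CV (and for which PK parameter), limits, interval and method produced 60. Correct any misstated input in the synopsis, Protocol 9.1 and SAP section 7.
2. If the stated inputs stand, replace the 80% in those three places with about 14% (95% CI) or about 36% (90% CI, with 80–125% limits) per comparison, and say which interval the figure uses.
3. Add the expected precision at 60 evaluable subjects: the 90% CI runs from the estimate divided by about 1.19 to the estimate multiplied by about 1.19; the factor for the 95% CI is about 1.23.
4. State the equivalence limits in the synopsis and Protocol 9.1, so that the power can be checked there, and name the parameter that the CV describes.

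The cost is wording in three places. Neither the analysis nor the planned enrolment has to change. If the inputs stand, the stated power becomes much less favourable, and the case for 60 subjects would have to rest on precision.

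Suggested wording if the inputs stand: *With 60 evaluable subjects, a within-subject CV of 61% and a true ratio of 1.05, the probability that the 95% CI for one comparison on one parameter lies within 80–125% is about 14% (about 36% for the 90% CI). The 90% CI is expected to span the estimate divided and multiplied by about 1.19.*
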